12.3 Prohibited Medications/Therapies

Prior to discontinuation of tagraxofusp, patients may not receive the following anticancer/antimyeloproliferative agents: JAKi (ruxolitinib, fadaratinib, and others), interferon- α , thalidomide, lenalidomide, cytotoxic chemotherapy agents (including 2-chlorodeoxyadenosine and other purine analogs), hypomethylating agents (5-aza, decitabine and others), tyrosine kinase inhibitors (including those which inhibit the BCR-ABL kinase such as imatinib), HU, and investigational anti-cancer agents.

Patients may not receive additional disease-modifying or cytoreductive agents such as danazol or anagrelide. Patients may not receive erythroid- or platelet-stimulating growth factors.

Hydroxyurea is prohibited during study participation except for cycle 1; Short-term treatment with HU beyond cycle 1 with approval of the Medical Monitor is permitted.

Ongoing corticosteroid therapy at doses of > 20 mg/day prednisone (or equivalent) for > 7 days is not permitted; however transient increases in corticosteroid doses in the setting of infections or other “stress” settings are allowed.

13 Adverse Events and Safety Evaluation

The AE reporting period for a patient treated in the study begins with provision of consent and is continuous through 30 days after the last tagraxofusp infusion. All AEs that occur in treated patients during the AE reporting period must be reported to the Sponsor or designee, whether or not the event is considered related to tagraxofusp. Any known untoward event that occurs beyond the AE reporting period (30 days after the last tagraxofusp infusion) that the Investigator assesses as related to tagraxofusp should also be reported as an AE.

All patients should be monitored for at least 1 hour (or longer at the Investigator’s discretion) following the administration of each tagraxofusp infusion. The Investigator or designated medical staff responsible for study conduct and safety evaluations, should be available during the administration of tagraxofusp and follow-up to assess, treat, or report as necessary any AE or SAE that may occur.

13.1 Definitions

All observed or volunteered AEs regardless of suspected causal relationship to tagraxofusp will be reported as described below.

13.1.1 Adverse Event (AE)

An AE is any untoward medical occurrence in a study patient who is administered a medicinal product (drug or biologic); the event may or may not have a causal relationship with the medicinal product. Examples of AEs include, but are not limited to the following:

- Clinically significant symptoms and signs including:
 - Worsening of signs and symptoms of the disease under study; disease progression without worsening of signs and symptoms as assessed by bone marrow aspiration or other methods should not be reported as AEs.
 - Signs and symptoms resulting from drug overdose, abuse, misuse, withdrawal, sensitivity, dependency, interaction, or toxicity.
 - All possibly related and unrelated illnesses, including the worsening of a preexisting illness.
 - Injury or accidents. Note that if a medical condition is known to have caused the injury or accident (hip fracture from a fall secondary to dizziness), the medical condition (dizziness) and the outcome of the accident (hip fracture from a fall) should be reported as 2 separate AEs.
- Abnormalities in physiological testing or physical examination findings that require clinical intervention or further investigation (beyond ordering a repeat confirmatory test).
- Laboratory abnormalities that meet any of the following (Note: merely repeating abnormal test, in the absence of any of the below conditions, does not constitute an AE. Any abnormal test result that is determined to be an error does not require reporting as an AE):
 - Test result that is associated with accompanying symptoms
 - Test result that requires additional diagnostic testing or medical/surgical intervention
 - Test result that leads to significant additional concomitant drug treatment or other therapy
 - Test result that is considered to be an AE by the Investigator or Sponsor

Note that veno-occlusive disease occurring post-SCT and any changes in visual acuity and/or color vision will be followed as AEs of special interest.

13.1.2 Serious Adverse Event (SAE)

An AE that meets one or more of the following criteria/outcomes is classified as serious:

- Results in death;
- Is life-threatening (at immediate risk of death);
- Requires admittance to the hospital or prolongation of existing hospitalization;
- Results in persistent or significant disability/incapacity;
- Results in congenital anomaly/birth disfigurements among the offspring of the patients;
- Events with medical significance or needing medical intervention to prevent the occurrence of any of the above events.

Medical judgment should be exercised in deciding whether expedited reporting is appropriate in other situations, such as important medical events that may not be immediately life-threatening or result in death or hospitalization, but may jeopardize the patient or may require intervention to prevent one of the other outcomes listed in the definition above. Serious also includes any other event that the Investigator or Sponsor judges to be serious, or which is defined as serious.

AEs associated with in-patient hospitalization, or prolongation of an existing hospitalization, are considered serious. Any initial admission, even if the duration is less than 24 hours is considered serious. In addition, any transfer within the hospital to an acute/intensive care unit is considered serious. However, the following hospitalizations should not be considered serious:

- Hospitalization or prolonged hospitalization in the absence of precipitating clinical AEs, as follows:
 - Admission for treatment of preexisting condition not associated with the development of a new AE or with a worsening of the preexisting condition
 - Administrative admission (e.g., for a yearly physical examination)
 - Protocol-specified admission during the study (e.g., admission for tagraxofusp treatment)
 - Preplanned treatments or surgical procedures
 - Admission exclusively for the administration of blood products

Progress of the disease under study (including signs and symptoms of progression) should not be reported as an SAE unless the outcome is fatal during the study or within the safety reporting period. If the disease under study has a fatal outcome during the study or within the safety reporting period, then the event leading to death must be recorded as an AE and as an SAE of CTCAE Grade 5 intensity. Disease progression is NOT an SAE; however some sequelae of disease progression (i.e., pain, thrombocytopenia) may be reported as AEs or SAEs (generally not related to investigational therapy).

The onset date of an SAE is defined as the date on which the event initially met serious criteria (e.g., the date of admission to a hospital). The end date is the date on which the event no longer met serious criteria (e.g., the date the patient was discharged from a hospital).

13.2 Period of Observation

Clinical signs and symptoms, and AEs (regardless of relationship to study drug) will be collected for treated patients continuously from provision of consent to 30 days following the last infusion of tagraxofusp. All SAEs and AEs judged to be related to study drug will be collected throughout the AE reporting period.

Conditions that the patient experienced prior to the provision of consent should be recorded in the patient medical history section of the eCRF. All the AEs should be followed-up at the Investigator's discretion until the symptoms dissipate or become stable even if AEs continue beyond the period of observation. AEs unresolved at the end of the observation period will be considered "ongoing" with an undetermined outcome; however, if after the period of observation completes but prior to the completion of the study, additional outcome information becomes available, it will be reported. The severity of the signs, symptoms, or AEs should be determined using the CTCAE, v4.03. A complete CTCAE list can be downloaded at <http://evs.nci.nih.gov/ftp1/CTCAE/About.html>.

All clinically meaningful abnormal test results should be retested. Abnormal test results that are difficult to associate with the study drug should be followed until normalized or until the abnormality could be clearly attributed to another cause. Abnormal test results should not be reported as AEs unless they meet the criteria outlined in [Section 13.1.1](#).

13.3 Pre-existing Conditions

A pre-existing condition will not be reported as an AE unless the condition worsens by at least one CTCAE grade during the study. The pre-existing condition, however, must be recorded in the medical history eCRF as a pre-existing condition and all related concomitant medication administered for the condition recorded in the concomitant medication eCRF.

13.4 Pregnancy

WOCBP and men with partners of childbearing potential must be using an adequate method of contraception to avoid pregnancy throughout the study and for up to 1 week after the study in such a manner that the risk of pregnancy is minimized. WOCBP include any female who has experienced menarche and who has not undergone successful surgical sterilization (hysterectomy, bilateral tubal ligation, or bilateral oophorectomy) or is not postmenopausal (defined as amenorrhea \geq 12 consecutive months; or women on hormone replacement therapy with documented serum follicle-stimulating hormone level \geq 35 mIU/mL). Even women who are using oral, implanted, or injectable contraceptive hormones or mechanical products, such as an intrauterine device or barrier methods (diaphragm, condoms, spermicides) to prevent pregnancy,

are practicing abstinence, or whose partner is sterile (e.g., vasectomy), should be considered to be of childbearing potential.

WOCBP must have a negative serum or urine pregnancy test during screening within 1 week before the first study drug dose. If the pregnancy test is positive, the patient must not receive study therapy and must not be enrolled in the study.

Sexually active WOCBP must use an effective method of birth control during the course of the study, in a manner such that the risk of failure is minimized.

Prior to study enrollment, WOCBP must be advised of the importance of avoiding pregnancy during study participation and the potential risk factors for an unintentional pregnancy. This information will be included in the ICF that must be signed by the patient.

In addition, all WOCBP or fertile men with partners of childbearing potential should be instructed to contact the Investigator immediately if they suspect they or their partner might be pregnant (e.g., missed or late menstrual period) at any time during study participation.

If following initiation of study drug, it is subsequently discovered that a patient is pregnant or may have been pregnant at the time of exposure to study therapy, including during at least 1 week after product administration, study therapy will be permanently discontinued in an appropriate manner. Exceptions to discontinuation may be considered for life-threatening conditions only after consultation with the Sponsor and Medical Monitor or as otherwise specified in this protocol. The Investigator must immediately notify the Sponsor and Medical Monitor of this event.

Protocol-required procedures for study discontinuation and follow-up must be performed on the patient unless contraindicated by pregnancy (e.g., x-ray studies). Other appropriate pregnancy follow-up procedures should be considered if indicated. In addition, the Investigator must report to the Sponsor follow-up information regarding the course of the pregnancy of the patient/patient's partner, including perinatal and neonatal outcome. Infants should be followed for a minimum of 8 weeks.

13.5 Documentation and Reporting of Adverse Events by Investigator

The Investigator is to report all directly observed AEs and AEs spontaneously reported by the patient using concise medical terminology. In addition, each patient will be questioned about AEs at each clinic visit following initiation of treatment. The question asked will be "Since your last clinic visit have you had any health problems?" or a similar question to assess health status.

The AE reporting period for this study begins after provision of written informed consent and ends 30 days after the last tagraxofusp infusion. All AEs are to be reported on the AE eCRFs.

All AEs that occur in study patients during the AE reporting period must be reported to the Sponsor, whether or not the event is considered study drug-related. In addition, any untoward

event that occurs beyond the AE reporting period that the Investigator assesses as related to the investigational product should also be reported as an AE.

Each AE is to be classified by the Investigator as serious or non-serious. This classification of the gravity of the event determines the reporting procedures to be followed. If a SAE occurs, reporting will follow local and international regulations, as appropriate.

For any event that meets one of the SAE criteria, the Investigator must notify the Safety Contact **within 24 hours** of the knowledge of the occurrence. To report the SAE, complete the SAE form and email to the Safety Contact (email address listed below) within 24 hours of awareness.

Safety Contact Information: E-mail: [REDACTED]

Each SAE should be followed until resolution, or until such time as the Investigator determines its cause or determines that, it has become stable.

Within 24 hours of receipt of follow-up information, the Investigator must update the SAE form and submit any supporting documentation (e.g., patient discharge summary or autopsy reports) to the Safety Contact via e-mail. All SAEs are also to be recorded in the eCRF.

The Sponsor will report AEs, which are unexpected and reported as serious and associated with use of the study drug, to the applicable regulatory authorities and all participating sites. For events that are fatal or life-threatening, unexpected, and associated with use of the investigational product, a 7-Day Alert Report will be submitted to the applicable regulatory authorities within 7 calendar days of receipt of the SAE information. For all other events that are serious, unexpected, and associated with the use of the investigational medicinal product, a written report will be made no more than 15 calendar days from the date the Sponsor learns of the event.

13.6 Assessment of Causal Relationship to Tagraxofusp

In this study, the investigational medicinal product is tagraxofusp. The relationship of an AE to the investigational product should be classified using the following guidelines:

- Related: A temporal relationship exists between the event onset and administration of tagraxofusp. It cannot be readily explained by the patient's clinical state, intercurrent illness, or concomitant therapies. In case of cessation of the dose, the event abates or resolves and reappears upon re-challenge.
- Not Related: Evidence exists that the AE has an etiology other than the study drug (e.g., pre-existing condition, underlying disease, intercurrent illness, or concomitant medication). This includes events that are considered probably not or not related to tagraxofusp. It should be emphasized that ineffective study drug treatment should not be considered as causally related in the context of AE reporting (in other words, disease progression is not considered an AE; however some sequelae of disease progression may be reported as AEs and should generally be reported as AEs not related to investigational therapy).

An Investigator who is qualified in medicine and has an active license to practice in the geographic location where the patient is being treated must make the determination of relationship to the investigational product for each AE. The Investigator should decide whether, in his or her medical judgment, there is a reasonable possibility that the event may have been caused by the investigational product. The following factors for study drug relationship should be referenced when making a determination of “related” or “not related.”

- The temporal sequence from study drug administration: The event should occur after the study drug is given. The length of time from study drug exposure to event should be evaluated in the clinical context of the event.
- Underlying, concomitant, intercurrent diseases: Each report should be evaluated in the context of the natural history and course of the disease being treated and any other disease the patient may have.
- Concomitant medication/therapy: The other medications the patient is taking or the treatment the patient receives should be examined to determine whether any of them might be recognized to cause the event in question. Transfusions of pRBCs or platelets after enrollment (first dose) will be captured as concomitant medication/therapy.
- Known response pattern for this class of study drug: Clinical and/or preclinical data may indicate whether a particular response is likely to be a class effect.
- Exposure to physical and/or mental stresses: The exposure to stress might induce adverse changes in the recipient and provide a logical and better explanation for the event.
- The pharmacology and pharmacokinetics of the study drug: The known pharmacologic properties (absorption, distribution, metabolism, and excretion) of the study drug should be considered.

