5.2 Data Safety Review Committee

A Data Safety Review Committee (DSRC), which will include investigators and representatives from the Sponsor, will convene periodically to review data from Stages 2 and 3A of the study. The DSRC will also convene in the event of identification of unexpected AEs, or AEs occurring at a frequency or severity not previously anticipated or following deaths on-study which are considered treatment related and/or not related to the underlying disease and sequelae.

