8.2.3.2 Chills, Anaphylaxis, and Hypersensitivity Reactions

Withhold tagraxofusp infusion for chills, anaphylaxis and hypersensitivity reactions.

Chills associated with tagraxofusp administration may be treated with meperidine 12.5-50 mg IV or morphine sulphate 1-2 mg IV (or equivalent doses of other opiates). Anaphylaxis and hypersensitivity reactions associated with rash, fever, urticaria, bronchospasm, and/or angioedema will be treated with 100 mg IV methylprednisolone (or an equivalent corticosteroid) and 25-50 mg IV diphenhydramine (or equivalent dose of another H₁-histamine antagonist). More severe symptoms will also be treated with 0.3 mL epinephrine (1:1000) IV once. Patients with anaphylactic (Grade 4) reactions or Grade ≥ 3 hypersensitivity reactions should not receive additional infusions of tagraxofusp.

In the setting of Grade 1-2 hypersensitivity reactions, administration of subsequent tagraxofusp infusions may be attempted provided that any systemic symptoms of the prior Grade 1-2 hypersensitivity reaction resolved within 24 hours with appropriate supportive measures. Premedication for patients with prior Grade 1-2 hypersensitivity reactions should include the agents specified in [Section 8.2.1](#); additional premedication may be provided at the Investigator's discretion and should be discussed with the Medical Monitor or designee. Please consult [Section 13.7](#) concerning recommended optimal reporting of tagraxofusp-related hypersensitivity reactions.

Blood (serum) samples (10 mL, for immunogenicity) will be collected anytime during the study when clinical manifestations are observed suggesting either an infusion related reaction or drug hypersensitivity.

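### Protocol 13.6 sets two conflicting causality standards: the Related bullet asks for recurrence on re-challenge with no exception, while the next paragraph asks only for a reasonable possibility

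*Protocol*

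**What the plan says.** Protocol 13.6 opens its causality rules with "The relationship of an AE to the investigational product should be classified using the following guidelines" and offers two categories.

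- **Related** has three sentences. The first is about timing: "A temporal relationship exists between the event onset and administration of tagraxofusp". The second is about other explanations for the AE: "It cannot be readily explained by the patient's clinical state, intercurrent illness, or concomitant therapies". The third is about stopping the drug: "In case of cessation of the dose, the event abates or resolves and reappears upon re-challenge".
- **Not Related** calls for evidence of a cause other than the study drug. It also takes in events thought probably not related.

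The following paragraph has a medically qualified, licensed investigator make the call, using medical judgment on whether "there is a reasonable possibility that the event may have been caused by the investigational product". It then lists factors to consult: timing, other disease, concomitant treatment, known class pattern, stress and pharmacology. Re-challenge is not among them.

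On re-exposure, Protocol 8.2.3.2 says that patients with Grade 4 anaphylaxis or Grade 3 or higher "hypersensitivity reactions should not receive additional infusions of tagraxofusp". Protocol 13.7 includes Grade 5, death, as a severity grade.

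**The concern.** A causality definition has to be one that every event can be tested against. The third sentence of the Related bullet applies once dosing stops, and it joins two conditions: the event goes away, and it comes back on re-exposure. It has no qualifier such as 'if re-challenged'. Stopping the drug is the situation in which re-exposure is least likely, and for one named class of reactions the protocol rules it out.

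A site that takes the bullet at its word therefore has a reason not to tick Related for a reaction that the next paragraph would have it call Related. Nothing in 13.6 says which text governs. The study has no control arm to show whether attribution has drifted, so the investigator's call is the only source for anything that depends on relatedness.

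**Working it through.** No arithmetic applies: neither document ties a rate, count or sample size to the causality definition. The check sets the two standards against the kinds of event that the protocol foresees. In each row, assume that timing fits and no other cause is evident.

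| Event | Related bullet, read literally | Reasonable-possibility test | Not Related |
|---|---|---|---|
| Dosing not stopped | Met; third sentence is not triggered | Can be Related | Not met |
| Dosing stopped, restarted, event recurs | Met | Can be Related | Not met |
| Grade 4 anaphylaxis or Grade 3 or higher hypersensitivity | Cannot be met: no further infusions under 8.2.3.2 | Can be Related | Not met |
| Other event that ends treatment for good | Cannot be met: no re-exposure | Can be Related | Not met |
| Fatal event | Cannot be met: it neither abates nor recurs. If death is not read as cessation of the dose, the sentence is silent | Can be Related | Not met |

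In the first two rows the standards agree. In the third and fourth, and in the fifth unless the sentence is read as silent, the bullet is not met while the second test can be, and Not Related is not met either because it needs evidence of another cause. That gives one section, two answers for the same event, and a gap between the categories.

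Next, what depends on the call:

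1. **Expedited reporting (Protocol 13.5).** The 7-day report for fatal or life-threatening unexpected events needs an association with the product. The 15-day rule reads "For all other events that are serious, unexpected, and associated with the use of the investigational medicinal product". Both are exposed.
2. **AEs beyond 30 days after the last infusion (Protocol 13 and 13.5).** These are to be reported if the investigator assesses them as related. This is exposed.
3. **Related-TEAE tables (SAP 4.4.2).** These are exposed. The SAP counts a missing relationship as related, but it does not alter a recorded Not Related.
4. **AEs up to 30 days (Protocol 13.5).** These are reported whatever the causality, and SAEs go to the safety contact within 24 hours on the same basis. They are not exposed.
5. **Other AE tables (SAP 4.4.2).** All TEAEs, Grade 3 or higher events, SAEs, discontinuations and deaths are tabulated without a causality filter. Hypersensitivity and capillary leak are found by MedDRA terms. These are essentially unaffected; the one narrow link is that a baseline event later judged drug-related counts as treatment-emergent.
6. **Safety committee (Protocol 5.2).** An ad hoc meeting also follows "following deaths on-study which are considered treatment related and/or not related to the underlying disease and sequelae". The second limb needs no Related call, and unexpected AEs trigger a meeting on their own. There is little exposure.

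Two minor uses remain: ophthalmology referral for drug-related visual change (Protocol 11.11) and an exception in the per-protocol definition (SAP 2.1). The point does not rest on either.

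**The case against.** The best case against is that the protocol, read as a whole, does not make re-challenge a condition. The categories are introduced as guidelines. The disputed sentence is conditional on the dose being stopped, and nothing says that all three sentences must be met. The instruction to decide on a reasonable possibility is in the same section. Elsewhere the protocol treats these reactions as attributable: 8.3.1 lists tagraxofusp-related anaphylaxis or Grade 3 or higher hypersensitivity as a reason to stop treatment, 13.7 explains how to report hypersensitivity judged related, and 5.2 and 13.5 contemplate deaths and fatal events attributed to the drug.

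Most of this stands. It shows what the authors intended, and many investigators will follow the second test. It does not remove the conflict, because the sentence has no exception and no text ranks the two standards.

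The direction of any error can also be disputed. Not Related is blocked on a literal reading too, so an event that fails the bullet is not thereby sent to the other category. That is fair: under-attribution is possible but not shown.

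A reader might infer more, namely that every severe hypersensitivity reaction and every fatal event is excluded from Related. The documents do not support that. It restates the most literal reading of one sentence as if it were an observed rate, and neither document contains causality data against which to test it.

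**Conclusion.** The point holds as an internal contradiction in Protocol 13.6, with a gap between its two categories. A site applying the bullet literally could leave a true reaction outside Related, and the sentence is hardest to satisfy for severe reactions that end dosing. How often this happened, if at all, is unknown. The material exposure is the related-TEAE tables, the 7- and 15-day reports, and collection of AEs more than 30 days after the last infusion. Because SAP 4.4.2 ends treatment-emergence at 30 days, those late events would not enter the related-TEAE tables in any case.

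The conclusion assumes that at least some sites read the bullet as written and do not default to the reasonable-possibility test. The documents do not say how sites were trained.

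A reader might also infer that any event without evidence of another cause should default to Related, and that SAP 4.4.2 already works this way. It does not: the SAP rule covers a missing relationship only, and such a default would be a new rule that neither document contains.

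**What to change.** In Protocol 13.6, state that an AE is Related when, in the investigator's judgment, there is a reasonable possibility that tagraxofusp caused it. Replace the third sentence of the bullet with a statement that de-challenge and re-challenge are supporting information where they occurred and are not a condition. The bar in 8.2.3.2 and every other dosing or stopping rule stay as they are.

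The cost is one paragraph in an amendment or a clarification letter to sites. The reported treatment-related AE rate may rise slightly.

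SAP Section 5 says that Stage 3A enrollment was not continued and that analysis follows once all patients have exited and the database is locked. The change can therefore help only calls still open. For calls already recorded, a note in the clinical study report beside the related-TEAE tables, saying that two standards were in force, is enough. A sponsor-prompted re-query of selected events in an open-label study could itself shift attribution, so it is not part of this recommendation.
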